### PK Parameter

### Definition

as:  $(C_{max,m}/C_{max,p})(MW_p/MW_m)$ , where  $C_{max,m}$  and  $MW_m$  are  $C_{max}$  and molecular weight of metabolite, respectively, and  $C_{max,p}$  and  $MW_p$  are  $C_{max}$  and molecular weight of parent lixivaptan, respectively. The following molecular weights are to be used in all MR parameter [MRCmax and MRAUC(0-14)] calculations:

lixivaptan: 473.93 g/mol

WAY-141624: 505.95 g/mol

WAY-138451: 488.92 g/mol

WAY-138758: 426.82 g/mol

MRAUC(0-14)

Ratio of metabolite  $AUC_{(0-14)}$  to parent lixivaptan  $AUC_{(0-14)}$ , calculated for all metabolites and corrected for molecular weight of metabolite and parent as:  $(AUC_{(0-14),m}/AUC_{(0-14),p})(MW_p/MW_m)$ , where  $AUC_{(0-14),m}$  and  $MW_m$  are  $AUC_{(0-14)}$  and molecular weight of metabolite, respectively, and  $AUC_{(0-14),p}$  and  $MW_p$  are  $AUC_{(0-14)}$  and molecular weight of parent lixivaptan, respectively.

Document: PK/PD STATISTICAL ANALYSIS PLAN

Author: [name] Version Number: 1.0

Version Date: 12 Aug 2019

Template No: CS\_TP\_BS016 - Revision 5 Reference: CS\_WI\_BS005

Effective Date: 01Apr2018

Palladio BiosciencesInsert Customer Name/ Logo PK/PD STATISTICAL ANALYSIS PLAN: PROTOCOL PA-102 Page 31 of 39

The following PK parameters (Table 4) will be calculated for diagnostic purposes, when appropriate, and listed but will not be summarized.

Table 4 Calculation of PK Parameters for Diagnostic Purposes

PK Parameter	Definition
λ z _low	The starting time point (h) of the time interval of the log-linear regression to determine $\lambda_{\text{Z}}. eq:log_log_log_log_log_log_log_log_log_log_$
λ z _upp	The ending time point (h) of the time interval of the log-linear regression to determine $\lambda_{\text{Z}}.$
t 1/2 , Interval	The time interval duration (h) of the log-linear regression to determine $\lambda_Z$ , calculated as $\lambda_Z$ _upp – $\lambda_Z$ _low.
t 1/2 , N	Number of data points included in the log-linear regression analysis to determine $\lambda_z$ . A minimum of 3 data points will be used for determination.
Rsq_adj	Adjusted coefficient of determination for calculation of $\lambda_z$ . If Rsq_adj <0.800, then $\lambda_z$ and parameters derived from it will be listed but flagged and excluded from summaries.
%AUC ex	Percentage of AUC (0-inf) obtained by extrapolation, calculated as $[(C_{last}/\lambda_z)/AUC_{(0-inf)}\times 100]. \   If the  \%AUC_{ex} \   is  greater  than  30.0\%  of  AUC_{(0-inf)}, \\ then  AUC_{(0-inf)}  will  be  listed  but  flagged  and  excluded  from  summaries.$

Document: PK/PD STATISTICAL ANALYSIS PLAN Author: [name]

Version Number:

1.0

Template No: CS\_TP\_BS016 - Revision 5

Version Date:

12 Aug 2019

Effective Date: 01Apr2018

Reference: CS\_WI\_BS005

Effective Bate. 01Apr2010

Palladio BiosciencesInsert Customer Name/ Logo PK/PD STATISTICAL ANALYSIS PLAN: PROTOCOL PA-102 Page 32 of 39

Table 5 lists the above non-diagnostic PK parameters to be calculated by Study Day and dosing interval.

Table 5 Calculation of PK Parameters at Specific Study Days and Dosing Intervals

Study Day & Dosing Interval	PK Parameter
Day 1 AM Dose	$C_{\text{max}}$ , $t_{\text{max}}$ , AUC(0-last), AUC(0-inf), $\lambda_{\text{Z}}$ , $t_{1/2}$ , CL/F, $V_{\text{Z}}/F$
Day 1 PM Dose	$C_{max}$ , $t_{max}$ , $AUC_{(0-last)}$
Day 7 AM Dose	$C_{max}\text{, }t_{max}\text{, }AUC_{(0\text{-last})}\text{, }CL/F\text{, }V_Z/F\text{, }RC_{max}\text{, }RAUC_{(0\text{-last})}$
Day 7 PM Dose	$C_{\text{max}}\text{, }t_{\text{max}}\text{, }AUC_{\text{(0-last)}}\text{, }AUC_{\text{(0-14)}}\text{, }\lambda_{\text{Z}}\text{, }t_{\text{1/2}}\text{, }MRC_{\text{max}}\text{, }MRAUC_{\text{(0-14)}}$

In accordance with molecular formula and formulation for lixivaptan, no dose adjustment calculations will be made for any molecular conversions between administered drug product and analyte measure.

A subject listing of individual PK parameters for lixivaptan and lixivaptan metabolites will be provided. Parameter listings will be based on the Safety Analysis Set. The PK parameters will be summarized by analyte, cohort (renal function/CKD stage/dose), Study Day, and dosing interval (AM/PM) using descriptive statistics as described in Section 6.1 and Section 8. Additional summarization will be made with further stratification by gender (male versus female), and, independently, by CKD stage within cohort. Parameter summaries will be based on the PK Analysis Set.

Scatter plots of individual and geometric mean PK parameters versus cohort will be presented for lixivaptan only, stratified by Study Day and dosing interval (AM/PM), based on the PK Analysis Set. Additional figure(s)/plot(s) will be made with further stratification by gender

Document: PK/PD STATISTICAL ANALYSIS PLAN
Author: [name]

Version Number:

1.0

Version Date:

12 Aug 2019

Template No: CS\_TP\_BS016 - Revision 5

Effective Date: 01Apr2018

Reference: CS\_WI\_BS005

Palladio BiosciencesInsert Customer Name/ Logo PK/PD STATISTICAL ANALYSIS PLAN: PROTOCOL PA-102 Page 33 of 39

(male versus female), and, independently, by CKD stage within cohort. Additional, graphical presentations of PK data may be added if further illustration of the PK results is deemed appropriate.

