### 7.2. ESTIMANDS

As per International Council for Harmonisation E9 (R1), the estimands for this study are described as follows:

Primary Estimand 1: See Non-PK/PD SAP.

Primary Estimand 2: The PK profile of lixivaptan and its major metabolites (WAY-141624, WAY-138451, WAY-138758) following first and multiple doses of lixivaptan in ADPKD subjects.

- Population: ADPKD subjects with at least one post-dose PK assessment and defined further through appropriate inclusion/exclusion criteria.
- Variables (or endpoints): PK concentrations and parameters (Cmax, tmax, AUC from time 0 until the last quantifiable concentration [AUC(0-last)], AUC

Document: PK/PD STATISTICAL ANALYSIS PLAN

Author: [name] Version Number: 1.0

Version Date: 12 Aug 2019

Template No: CS\_TP\_BS016 - Revision 5 Reference: CS\_WI\_BS005

Effective Date: 01Apr2018

Palladio BiosciencesInsert Customer Name/ Logo PK/PD STATISTICAL ANALYSIS PLAN: PROTOCOL PA-102 Page 17 of 39

extrapolated to infinity [AUC(0-inf)], AUC from time 0 until 14 hours post-dose [AUC(0-14)], terminal elimination phase half-life [ $t_{1/2}$ ], apparent terminal elimination rate constant [ $\lambda_Z$ ], apparent systemic clearance after extravascular dosing [CL/F; lixivaptan only], and apparent volume of distribution after extravascular dosing [ $V_Z$ /F; lixivaptan only]).

- Strategy for addressing intercurrent event: Regardless if subject discontinues treatment prematurely.
- Population-level summary: Descriptive differences in PK parameter means of the four cohorts.

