Template No: CS\_TP\_BS016 - Revision 5 Reference: CS\_WI\_BS005

Effective Date: 01Apr2018

Palladio BiosciencesInsert Customer Name/ Logo PK/PD STATISTICAL ANALYSIS PLAN: PROTOCOL PA-102 Page 25 of 39

Table 3) will be estimated for lixivaptan and lixivaptan metabolites by non-compartmental methods using validated software and actual elapsed time from dosing. See Table 5 for specific Study Days and dosing intervals for which each PK parameters will be calculated. A minimum of 3 quantifiable post-dose concentration-time data points will be required for calculation of PK parameters.

Document: PK/PD STATISTICAL ANALYSIS PLAN

Author: [name] Version Number: 1.0
Version Date: 12 Aug 2019

Template No: CS\_TP\_BS016 - Revision 5 Reference: CS\_WI\_BS005

Effective Date: 01Apr2018

Palladio BiosciencesInsert Customer Name/ Logo PK/PD STATISTICAL ANALYSIS PLAN: PROTOCOL PA-102 Page 26 of 39

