# **Table 3 Estimation of PK Parameters**

Dar	1	A	T.	Æ	
Dav		Α	. 13	/1	:

PK Parameter	Definition
C max	Maximum observed plasma drug concentration (ng/mL), obtained
	directly from the observed concentration versus time data.
t max	Time to reach maximum plasma concentration (h), obtained directly from
	the observed concentration versus time data.
AUC (0-last)	Area under the concentration-time curve from time 0 until the last
	quantifiable concentration (ng·h/mL), calculated by linear up/log down
	trapezoidal summation.
AUC (0-inf)	Area under the concentration-time curve from time 0 extrapolated to
	infinity (ng·h/mL), calculated by linear up/log down trapezoidal
	summation and extrapolated to infinity by addition of the last
	quantifiable observed concentration divided by the elimination rate
	constant: $AUC_{(0-last)} + C_{last}/\lambda_z$ .
$\lambda_{Z}$	Apparent terminal elimination rate constant (1/h), determined by linear
	regression of the terminal points of the log-linear concentration-time
	curve. The Best Fit method utilized by WinNonlin will be used to identify
	the terminal linear phase of the concentration-time profile, with visual
	assessment and adjustment of the selected data points by the PK scientist
	if warranted. A minimum of 3 data points will be used for determination.
t 1/2	Apparent terminal elimination phase half-life (h), determined as $ln2/\lambda_Z$ .
CL/F	Apparent systemic clearance after extravascular dosing (L/h), calculated

Document: PK/PD STATISTICAL ANALYSIS PLAN

Author: [name] Version Number:

1.0 12 Aug 2019

Template No: CS\_TP\_BS016 – Revision 5 Reference: CS\_WI\_BS005

Effective Date: 01Apr2018

 $Copyright © 2009, 2010, 2012, 2016, 2018 \ IQVIA. \ All \ rights \ reserved. \ The \ contents \ of \ this \ document \ are \ confidential \ and \ proprietary \ to \ IQVIA \ Holdings \ Inc. \ and \ its \ subsidiaries. \ Unauthorized \ use, \ disclosure \ or \ reproduction \ is \ strictly \ prohibited.$ 

Version Date:

Palladio BiosciencesInsert Customer Name/Logo PK/PD STATISTICAL ANALYSIS PLAN: PROTOCOL PA-102 Page 27 of 39

PK Parameter	Definition	
	as (lixivaptan only):	
	
 
Day 1 AM: dose divided by AUC(0-inf), or
 
	
	
 
Day 7 AM: dose divided by AUC(0-last).
 
	
V z /F	Apparent volume of distribution following extravascular dosing (L), calculated as CL/F divided by $\lambda_Z$ (lixivaptan only).	

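### The 10-hour Day 1 AM profile cannot support the planned terminal half-life and AUC(0-inf) for the longest-lived metabolite, and the 30% extrapolation rule does not say whether lixivaptan CL/F and Vz/F follow AUC(0-inf) out of the summaries

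*SAP*

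**What the plan says.** PK/PD SAP 14.2 introduces a parameter set that "will be estimated for lixivaptan and lixivaptan metabolites by non-compartmental methods using validated software and actual elapsed time from dosing". For the Day 1 AM dose, Table 5 lists Cmax, tmax, AUC(0-last), AUC(0-inf), lambda-z, t1/2, CL/F and Vz/F. In Table 3 only CL/F and Vz/F are limited to lixivaptan. The text below Table 5 adds: "The PK parameters will be summarized by analyte, cohort (renal function/CKD stage/dose), Study Day, and dosing interval (AM/PM) using descriptive statistics". Protocol 2.2.1 makes AUC(0-inf), lambda-z and t1/2 primary endpoints for the parent and each metabolite.

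Footnote 13 of protocol Table 12-1 places the AM samples at 0, 1, 2, 4, 6, 9 and 10 h, the last of them just ahead of the evening dose. Protocol 3.1.1 justifies sampling to 96 h after the final dose as roughly four half-lives of the longest-lived metabolite, which it does not name.

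Table 4 holds two screening rules of different reach:
- If Rsq_adj is below 0.800, lambda-z goes, and "parameters derived from it will be listed but flagged and excluded from summaries" applies to whatever depends on it.
- If more than 30.0% of AUC(0-inf) is extrapolated, AUC(0-inf) goes. No other parameter is named.

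Table 4 quantities are "listed but will not be summarized". Day 1 CL/F is defined through AUC(0-inf) ("Day 1 AM: dose divided by AUC"), and Vz/F is CL/F over lambda-z. The PK estimand in 7.2 is summarised as "Descriptive differences in PK parameter means of the four cohorts". Section 6.1 requires at least 3 values before a mean is shown.

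**The concern.** A 10 h window is short against a half-life near 24 h. For that metabolite the plan promises a primary endpoint, AUC(0-inf), that its own rule will remove, and Day 1 AM is the only place where AUC(0-inf) is derived. Lambda-z and t1/2 are not covered by the 30% rule. A terminal slope fitted to three points over a few hours can pass on goodness of fit while describing very little of the decline. Table 4 records the regression span ("The time interval duration (h) of the log-linear regression to determine" lambda-z) but sets no minimum for it.

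For lixivaptan the problem is consistency. If some profiles exceed 30%, AUC(0-inf) loses them while CL/F and Vz/F, built on the same rejected AUC, keep them. The summary tables would show different n without the cause. The profiles lost tend to be those with long half-lives and high exposure, which bears on the comparison between CKD groups.

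**Working it through.** **Implied half-life.** Protocol 3.1.1: 96 h / 4 = 24 h. Share of one half-life covered on Day 1 AM: 10 / 24 = 0.42.

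**Extrapolated share.** For a mono-exponential curve the part of AUC(0-inf) beyond 10 h is 2^(-10/t1/2). At 24 h this is 2^(-0.417) = 0.749. It is a lower bound: formation half-lives of 0.5 to 4 h give 0.765 to 0.864. The 30% limit is met only if t1/2 is at most 10 x ln 2 / ln(1/0.30) = 6.931 / 1.204 = 5.76 h. With first-order input the limit falls to 5.36 h (rate 1.5 per h) or 4.41 h (0.5 per h).

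**What passes for a 24 h metabolite.** The model simulates the Day 1 schedule with linear-up/log-down AUC and the best adjusted R-squared fit on 3 or more points after Cmax. Assumed, because the documents do not give them: 41% CV in clearance (the SAP's AUC figure for lixivaptan, borrowed), 5-15% residual noise, and the formation rate.

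| Formation | Profiles with Rsq_adj >= 0.800 | Median t1/2 of those kept | Chance that a cohort of 8 has 3 values |
|---|---|---|---|
| 1.0-1.5 per h | about 10-45% | about 10-18 h | 4-77% |
| 0.5 per h | 3-6% | 13.8-23.1 h | under 1% |
| from circulating parent, parent t1/2 1.5-6 h | 0-1.4% | not informative | 0.01% or less |

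AUC(0-inf) survives the 30% rule in about 0.3% of profiles or fewer. If every subject has exactly 24 h and formation is rapid (formation half-life 0.5 h), the kept median is 21.6, 15.2 and 11.4 h at noise of 5, 10 and 15%. The shortening therefore grows with noise and is partly a selection of subjects whose half-life is truly shorter. On the Day 7 PM profile to 96 h, 99-100% pass, with a median of 23.8-24.1 h.

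**Lixivaptan.** No half-life is stated, so a range is shown. Clearance log-variance 0.08 plus bioavailability 0.075 gives 0.155, the SAP's figure for AUC. Residual noise is 5-10%, and results are for absorption 1.5 / 0.5 per h.

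| Median t1/2 | AUC(0-inf) kept | CL/F values from a rejected AUC |
|---|---|---|
| 1.5-2 h | 97-100% (both rates) | few |
| 3 h | 96-97% / 76-83% | 3% / 16-17% |
| 4 h | 81-83% / 44-48% | 17% / 43-50% |

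The geometric mean of the kept AUC(0-inf), relative to truth, is 0.95 / 0.91-0.92 at 3 h and 0.89 / 0.80-0.81 at 4 h. Not all of that is exclusion. At rate 1.5 per h the value is already 0.947 at 2 h with 99.9% kept, which is trapezoid error from sparse early samples. Exclusion adds to it from about 4 h at the fast rate and from about 3 h at the slow rate (0.98 at 2 h).

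If CKD3 clearance were one third lower (assumed; true exposure ratio 1.50), the kept AUC(0-inf) would show 1.34-1.35 / 1.22-1.25 at 3 h and 1.22-1.25 / 1.13-1.19 at 4 h.

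**The case against.** The strongest reply is that the plan already protects itself. The 30% rule and the 3-value minimum leave an empty metabolite AUC(0-inf) cell, which misleads nobody. The protocol qualifies the parameters as whenever possible, and the PK scientist may adjust the fitted points by eye. Terminal parameters are assigned to the Day 7 PM profile, where they are planned for every analyte. Metabolite Day 1 lambda-z feeds no planned ratio or plot. Excluded values and the extrapolated percentage appear in the subject listings, so with 8 subjects per cohort the cause can be traced.

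Most of this stands, and it rules out some tempting inferences. A reader might infer that the plan will print a falsely short metabolite half-life. That needs rapid, mainly first-pass formation; if the metabolite forms from circulating parent, almost nothing passes. A reader might infer that the reason for exclusion is hidden. It is missing from the summary tables only. A reader might extend 24 h to all three metabolites, but the protocol says it of one.

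The reply does not remove the core. None of the safeguards sets a minimum span for lambda-z, an empty cell still leaves a primary endpoint undelivered, and the two rules differ in scope with no reason given.

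**Conclusion.** The concern holds in this form. From the documents alone: a 10 h profile covers about 0.4 of the implied 24 h half-life, at least 75% of that metabolite's AUC(0-inf) is extrapolated, and the SAP's own rule will exclude essentially all of it. Its Day 1 lambda-z and t1/2 will usually be absent as well. Where formation is rapid (1.0-1.5 per h, assumed), they would come from about 10-45% of profiles, with a median near 10-18 h instead of 24 h.

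The scope gap for CL/F and Vz/F is a matter of wording and is certain. Its effect is not. It is negligible if the lixivaptan half-life is near 2 h and material from about 3-4 h, depending on absorption. A reader might conclude that the lixivaptan cohort comparison is biased; the documents give no half-life, so they support only a caution. A reader might also conclude that CL/F from all profiles is the better cohort comparison. That does not follow, since it would rely on AUCs the SAP itself rejects. For those profiles the 10th to 90th percentile of estimated over true AUC(0-inf) is 0.82-1.56 at a half-life of 8 h, even under a mono-exponential model that favours extrapolation.

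**What to change.** 1. In PK/PD SAP Table 5, list but do not summarise Day 1 AM lambda-z, t1/2 and AUC(0-inf) for any metabolite whose half-life a 10 h profile cannot characterise. Name the longest-lived metabolite as one of them and write the criterion down in advance. Take metabolite t1/2 from the Day 7 PM profile to 96 h, which is already planned. Record the change to the primary endpoints in PK/PD SAP 3.3 and, if it is judged major, in a protocol amendment under protocol 7.7.
2. In Table 4, state whether the 30% rule covers Day 1 CL/F and Vz/F. Either extend it, so that all three parameters use the same subjects, or keep CL/F and Vz/F flagged and give the reason. Show the number excluded by each rule beside AUC(0-inf), CL/F and Vz/F.
3. Add a caution that a Day 1 AUC(0-inf) cohort difference may be understated where subjects were excluded for extrapolation. In section 15.2, fix AUC(0-last) in advance as the Day 1 exposure measure for the plots, in place of a choice made on appropriateness.

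Cost: SAP wording and a few table columns, with no new samples. Metabolite AUC(0-inf) becomes listing-only where it cannot be estimated, and the amendment question has to be decided and recorded.

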### 15. PHARMACODYNAMIC ANALYSIS

### 15.1. PHARMACODYNAMIC ENDPOINTS

The following are PD endpoints:

- Urine osmolality
- Specific gravity by refractometer
- Specific gravity by dipstick
- (24-hour) urine output
- (24-hour) fluid intake
- Fluid balance
- Total kidney volume (TKV)
- Liver volume (LV)
- Plasma copeptin
- Estimated glomerular filtration rate (eGFR); calculated by the 2009 Chronic Kidney
   Disease Epidemiology Collaboration (CKD-EPI) equation presented in Appendix 1 of the protocol.

A listing of all PD sample collection times will be provided. Subject listings of all PD data will be

Document: PK/PD STATISTICAL ANALYSIS PLAN

Author: [name] Version Number: 1.0

Version Date: 12 Aug 2019

Template No: CS\_TP\_BS016 - Revision 5 Reference: CS\_WI\_BS005

Effective Date: 01Apr2018

Palladio BiosciencesInsert Customer Name/Logo PK/PD STATISTICAL ANALYSIS PLAN: PROTOCOL PA-102 Page 34 of 39

presented for the observed values and change from baseline, based on the Safety Analysis Set. The observed value and the change from baseline in the PD endpoints will be summarized by cohort (renal function/CKD stage/dose), Study Day, dosing interval, and/or at each scheduled time point, as applicable, using descriptive statistics as described in Section 6.1 and Section 8. Additional summarization will be made with further stratification CKD stage within cohort. Pharmacodynamic summaries will be based on the PD Analysis Set. Any BLQ concentrations will be treated as 1/2 × LLOQ for the computation of change from baseline and descriptive statistics.

Any values after first administration of study drug are regarded as post-baseline values. Except for urine osmolality, the baseline value is the last value observed prior to first administration of study drug. For urine osmolality assessments, the baseline value for each time point after first administration of study drug is the value observed at the corresponding time point on Day -1 (or Day 1 for the AM predose assessment only).

The number and percentage of subjects who show uninterrupted suppression of urine osmolality over 24 hours, defined as spot urine osmolality <300 mOsm/kg at each time point during a 24-hour measurement period, as well as over 14 hours following the PM dose, will be determined for Day -1, Day 1, and Day 7 by dose and by cohort. The above summary will additionally be presented similarly for subjects who show uninterrupted urine osmolality ≤250 mOsm/kg over 24 hours or 14 hours (PM). The 24-hour measurement periods will be calculated as follows:

- For Day -1, from time = 0 on Day -1 until time = 0 (AM predose) on Day 1;
- For Day 1, from time = 1 h on Day 1 until time = 0 (AM predose) on Day 2; and
- For Day 7, from time = 1 h on Day 7 until time = 0 on Day 8

PK/PD STATISTICAL ANALYSIS PLAN Document:

Author: [name] Version Number: 1.0 Version Date: 12 Aug 2019

Template No: CS\_TP\_BS016 - Revision 5 Reference: CS\_WI\_BS005

Effective Date: 01Apr2018

Palladio BiosciencesInsert Customer Name/Logo PK/PD STATISTICAL ANALYSIS PLAN: PROTOCOL PA-102 Page 35 of 39

In addition, the number and percentage of subjects with spot urine osmolality <300 mOsm/kg at each time point during the three 24-hour measurement periods (Day -1, Day 1, and Day 7) will be determined by dose and by cohort. The above summary will additionally be presented similarly for subjects who with spot urine osmolality ≤250 mOsm/kg at each time point.

Figure(s) of mean (±SD) urine osmolality versus time by Day (overlaid within plot), cohort, and CKD stage within cohort, will be produced. Figure(s) of mean (±SD) PD endpoint versus Day by cohort and CKD stage within cohort will be produced for urine output, fluid intake, fluid balance, TKV, LV, and plasma copeptin. All the above PD figures will use a linear scale for the PD dependent variable, using the observed values.

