6.1.7 Urine Osmolality and Specific Gravity

Spot urine collections will be obtained at the timepoints specified in the study schedule of assessments ([Table 12-1](#)). Subjects will be asked to completely empty their bladders 15 minutes prior to each scheduled spot urine collection, after which each subject will have 30 minutes to provide a spot urine specimen for the determination of urine osmolality and specific gravity. The goal is to provide a spot urine sample within 30 minutes. Subjects who will not be able provide a sample within the initial 30 minutes after voiding will be given an additional 30 minutes to do so and the different sampling time will be recorded.

Spot urine samples will be used to construct the time course of urine osmolality and specific gravity upon dosing. Urine osmolality measurements will be performed at the central laboratory, whereas the determination of urine specific gravity will be performed in the CRU in two manners: using dipsticks provided by the Sponsor and using existing CRU equipment, where available.

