7.7.2 Pharmacodynamic Analyses

The change from baseline in urine osmolality, serum creatinine, plasma copeptin, TKV and LV after multiple doses of lixivaptan will be summarized by renal function group (CDK1/2 and CDK3), and at each scheduled time point using descriptive statistics (n, mean, SD, median, minimum, and maximum).

Except for the case of urine osmolality, the baseline value is the last value observed prior to first administration of study drug and any values after first administration of study drug are regarded as post-baseline values. The change-from-baseline variables will be calculated as the post-baseline value minus the value at baseline.

For urine osmolality assessments, the baseline value for each time point after first administration of study drug is the value observed at the corresponding time point on Day -1 (or Day 1 for the AM predose assessment only). Any values after first administration of

study drug are regarded as post-baseline values. The change-from-baseline variables will be calculated as the post-baseline value minus the value at baseline. The number of subjects who show suppressed urine osmolality, defined as spot urine osmolality < 300 mOsm/kg for 24h, on Day 1 (AM predose) compared with Day 8 (AM predose) will be determined.

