Day 2, 4 and 6: 0 hours (immediately before AM dose);
Day 7: 0, 1, 2, 4, 6, 9, 10, 11, 12, 14, and 16 hours post AM dose. The collections at 0 and 10 hours are immediately before the AM and PM doses, respectively;
Day 8: 0 hours (corresponding to 24 hours after AM dose on Day 7) and 10 hours (corresponding to 24 hours after PM dose on Day 7);
Day 9: 48 hours after PM dose on Day 7;
Day 11: 96 hours after PM dose on Day 7.
- ¹⁴ Urine will be collected for determination of spot urine osmolality and urine specific gravity at the following timepoints:
Day -1: 0 (start), 1, 2, 4, 6, 9, 10, 11, 12, and 14 hours.

Day 1: 0, 1, 2, 4, 6, 9, 10, 11, 12, and 14 hours post AM dose. The collections at 0 and 10 hours are immediately before the AM and PM doses, respectively;

Day 2: 0 hours (immediately before AM dose on Day 2, corresponding to 24 hours after AM dose on Day 1).

Day 7: 0, 1, 2, 4, 6, 9, 10, 11, 12, and 14 hours post AM dose. The collections at 0 and 10 hours are immediately before the AM and PM doses, respectively;

Day 8: 0 hours (corresponding to 24 hours after AM dose on Day 7).

Note: Subject may not be able to void at all timepoints - see [Section 6.1.7](#). For all voids, the volume (mL) and the date and time of void will be recorded.

- ¹⁵ Record daily urine output on Day -1, Day 1 and Day 7. On Day -1, measurement will begin 24 hours before the expected time of first study medication on Day 1 AM. On Day 1 and Day 7, measurements will begin immediately before the AM dose and will continue for 24 hours into the morning of Day 2 and Day 8, respectively.
- ¹⁶ Blood samples for determination of plasma copeptin will be taken at approximately the same time of day (in the morning and, on dosing days, before the lixivaptan dose).
- ¹⁷ Subjects will be admitted to the CRU in the evening of Day -2 or in the morning of Day -1. For subjects admitted to the CRU on Day -2, the Screening period will be until Day -3. For subjects admitted to the CRU on Day -1, the Screening period will be until Day -2.

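### PK/PD SAP 15.1 gives specific gravity one predose baseline, so 18 of 21 scheduled changes per method are not matched on nominal time, although osmolality from the same sample is (minor)

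*SAP*

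**What the plan says.** Protocol 7.7.2 plans change-from-baseline summaries for five measures: "The change from baseline in urine osmolality, serum creatinine, plasma copeptin, TKV and LV after multiple doses of lixivaptan will be summarized". Its baseline rule has one exception: "Except for the case of urine osmolality, the baseline value is the last value observed prior to first administration of study drug". Each osmolality value is instead compared with the reading at the same time point on Day -1, or with Day 1 for the morning predose value.

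PK/PD SAP 15.1 has a longer endpoint list. Specific gravity by refractometer and specific gravity by dipstick are two entries of their own, separate from urine osmolality. The summaries cover the list as a whole: "The observed value and the change from baseline in the PD endpoints will be summarized by cohort". The subject listings also carry change from baseline. The baseline sentence repeats the protocol's exception: "Except for urine osmolality, the baseline value is the last value observed prior to first administration". The time-matched rule that follows it names osmolality only.

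Protocol 6.1.7 gives both measures one purpose: "Spot urine samples will be used to construct the time course of urine osmolality and specific gravity upon dosing". Osmolality is measured centrally. Specific gravity is read at the site in two ways, "using dipsticks provided by the Sponsor and using existing CRU equipment, where available". Footnote 14 to protocol Table 12-1 sets one schedule for both: "Urine will be collected for determination of spot urine osmolality and urine specific gravity at the following timepoints". That schedule includes ten readings on Day -1.

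**The concern.** In protocol 7.7.2 the exception is complete. Of the five measures listed there, only osmolality has a within-day profile. Serum creatinine and copeptin are drawn in the morning, and the MRI volumes have one value per visit. The SAP then added a second measure with a within-day profile and did not extend the exception to it.

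Read literally, each specific-gravity value between 1 h and 14 h is compared with a single morning predose reading, so its change mixes time of day with drug effect. The osmolality change from the same sample does not have that feature. The two sets of change tables would describe the same urine under different baseline rules, and the documents give no reason for the difference. What the specific-gravity tables would lack is the within-subject change, and its SD, at matched nominal times.

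**Working it through.** The documents state no figure on this point, so this is a count from footnote 14 of protocol Table 12-1 with the 15.1 rule applied to each scheduled reading. Times are nominal hours: from the start of Day -1, and after the morning dose on Days 1 and 7.

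**Baseline under 15.1.** The last scheduled reading before the first dose is Day 1, 0 h.

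**Post-dose readings per subject and method:**

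| Day | Readings | At 0 h (matched) | At 1-14 h (not matched) |
|---|---|---|---|
| 1 | 1, 2, 4, 6, 9, 10, 11, 12, 14 h = 9 | 0 | 9 |
| 2 | 0 h = 1 | 1 | 0 |
| 7 | 0, 1, 2, 4, 6, 9, 10, 11, 12, 14 h = 10 | 1 | 9 |
| 8 | 0 h = 1 | 1 | 0 |
| Total | 21 | 3 | 18 |

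Share not matched: 18/21 = 85.7%. One reading is the baseline for all 21 changes.

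**The same 21 readings under the osmolality rule.** Nine Day -1 readings (1 to 14 h) serve two changes each, and Day 1 0 h serves three: 9 x 2 + 1 x 3 = 21. Ten baseline readings are used, all already scheduled, and 0 of 21 changes are unmatched.

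**Effect of missing baseline readings:**

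| Missing reading | Current rule | Time-matched rule |
|---|---|---|
| Day 1, 0 h | Baseline falls back to Day -1, 14 h. It matches only 14 h on Days 1 and 7, so 21 - 2 = 19 are unmatched (90.5%). All 21 can be calculated. | The three 0 h changes are lost. |
| One Day -1 reading at 1-14 h | Nothing lost if Day 1, 0 h is present. | Two changes lost. |
| All nine Day -1 readings at 1-14 h | Nothing lost if Day 1, 0 h is present. | 9 x 2 = 18 changes lost. |

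**Other endpoints in the 15.1 list.** Copeptin and eGFR rest on morning samples. Urine output, fluid intake and fluid balance have a single Day -1 value. The MRI volumes have one value per visit. The general rule creates no within-day mismatch for any of these, so the gap is confined to specific gravity.

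**The case against.** **No named result depends on it.** Specific gravity is absent from the protocol objectives, the secondary endpoints (2.2.2) and the PD parameters (7.2). It is also absent from the osmolality suppression analyses and the named figures in SAP 15.1, and from the PK/PD plots in 15.2. No formal comparison of specific-gravity change with osmolality change is planned. This stands, and it is why the point is minor.

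**The data are kept.** SAP 15.1 also requires observed-value summaries and subject listings of all PD data. A group-level comparison at matched times, and each subject's matched difference, can be derived from them. This stands too.

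**The baseline is conventional, and matching does not isolate drug effect.** A last-predose baseline is common practice. Under protocol 5.9, subjects keep their usual fluid intake on Day -1 but aim for 4-5 litres a day on drug. Protocol 5.3 specifies fasting around the Day 1 and Day 7 doses and states none for Day -1. A matched baseline leaves these differences in place. That limits what the fix achieves. It does not explain why two measures from one sample should follow different rules.

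**Matching has a cost.** Footnote 14 warns: "Subject may not be able to void at all timepoints". A reader might infer from the Day 1 0 h case, with 19 changes against 3, that the matched rule is also the more robust to missing samples. The documents do not support that. The 19 are calculable but unmatched, while the 3 are lost. A missing Day -1 reading at 1-14 h costs two changes under the matched rule and none under the current one.

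**The wording may already cover it.** Table 12-1 schedules specific gravity under its osmolality row, so the authors may have meant the exception to include it. SAP 15.1 also summarizes by day and time point as applicable, and the output shells are not in the documents. None of this settles the matter. Section 15.1 lists the measures separately and names only osmolality in the exception. The qualifier concerns how summaries are grouped and does not set a baseline. SAP 6.3 is a default that yields to 15.1 and is not time-matched either. SAP 3.3 says in general terms that the SAP clarifies which endpoints are PD endpoints, which covers adding specific gravity to the list but not its change analysis or baseline rule.

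**Conclusion.** The inconsistency is real and minor. As written, 18 of 21 scheduled post-dose specific-gravity changes per method have a baseline from another nominal time, while osmolality from the same sample is matched. The 0 h changes on Days 2, 7 and 8 are sound, and the osmolality analyses and observed specific-gravity values are untouched.

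The count assumes that 15.1 is applied literally and that the Day 1 predose sample is obtained. It counts scheduled readings, so missed voids would lower the actual numbers.

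Three stronger readings are not supported:

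- A reader might double the count across the two methods. Both methods read the same samples, so that adds no information.
- A reader might speak of mismatched clock times. Footnote 14 fixes hours from the start of Day -1 and hours after the morning dose, so the mismatch is in nominal time.
- A reader might infer a bias of known direction. The documents give neither the direction nor the size of any time-of-day component in specific gravity.

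**What to change.** In PK/PD SAP 15.1, extend the exception to name urine specific gravity by both methods alongside urine osmolality. Apply the time-matched Day -1 baseline (Day 1 for the morning predose value) to specific gravity wherever a reading exists at the matching time point. In SAP 3.3, record that change from baseline in specific gravity is an addition to protocol 7.7.2, and state its baseline rule.

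The cost is one phrase in 15.1 and one line in 3.3, with no new sampling. By schedule, the unmatched count falls from 18 to 0 of 21 per method. The SAP should acknowledge three limits:

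- Each missing Day -1 reading at 1-14 h loses two changes, and a missing Day 1 0 h reading loses three.
- Where a site has no equipment of its own, matched changes will exist by dipstick only.
- Matching removes the time-of-day component, not the differences in fluid intake and stated fasting between Day -1 and the dosing days.
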